3.3 Subject enrollment

Patients will be identified by Horizon Analytics for the study. Seven hundred patients will be allocated to be eligible to receive the intervention. Patients allocated to the intervention group will be contacted by phone by [REDACTED] pharmacists and will be asked to provide informed consent to participate in the intervention. Verbal consent will be documented by the clinical pharmacist in [REDACTED] medical record. In addition, all calls will be recorded and available for auditing should re-confirmation of verbal consent be required. Seven hundred patients will also be identified by Horizon Analytics as a control group for analyses purposes only; these patients will not be contacted.

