8.2 Sample size estimate

We anticipate that identification of at least 700 individuals in the intervention group and control group should be sufficient to detect an average change of 0.5% in A1c, assuming an $\alpha=0.05$, $1-\beta=0.80$, A1c standard deviation=1.9, and a verbal informed consent rate of 45%, including clustering and non-differential loss-to-follow up between the study groups (Table 5). With this sample size, we should also have the ability to detect differences in the adherence outcomes (Table 6).

Based on feasibility information from Horizon, we anticipate that of the 315 patients in the intervention group who are likely to be reached by pharmacists (45%), at least 236 will have usable follow-up data. This proportion of reached patients has been observed in prior, pilot studies that have used a similar approach.²⁵ In order to observe an overall A1c difference of 0.5% in the study population, these contacted patients must have a underlying mean A1c change of ~0.49% (Figure 3). This difference is in line with what clinical guidelines consider to be a clinically meaningful difference in glycaemic control. This A1c difference has been observed in prior work with clinical pharmacists.⁸ This sample size would also provide enough patients for the predictive analytics work, given the relative non-rare nature of the study outcomes (glycemic control and medication adherence).

Table 5. Justification: A1c power calculation parameters and ranges

Range of parameters: input ranges	A1c difference: 0.5% Sample size (N range)/group
A1c SD: 1.9-->N1	228
Intra-cluster correlation (N ₂ =N ₁ * 1.03)	235
Loss-to-follow-up (LTF): 15-30%	(best case: 276, worst case: 335)

Date

(N ₃ =N ₂ /[1-rate])	
Pharmacist contact rate: 35-50% (N ₄ =N ₃ /rate)	(best case: 552, worst case: 959)
Total	45% reach rate and 25% LTF: 696 patients/arm

Power (1-β): 0.80; Alpha (α): 0.05

Explanation of study parameters – Primary outcome (A1c)

- 1) Standard deviation of A1c: ranges between 1.0 and 2.0, depending on study length and average baseline A1c values. The most commonly cited value is 1.9, assuming equal variances between the groups. This would be non-differential between study groups.
- 2) Intra-cluster correlation: Other studies have also incorporated intra-cluster correlation (ICC) within PCP clinics (~0.03 for small pilot studies). This would be non-differential between study groups.

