1.3 Number of subjects

In total, 1,400 subjects were randomized in a 1:1 ratio to the intervention or control group. Our study was designed to be sufficiently powered to detect small but clinically meaningful changes in the primary outcome of HbA1c change.

We considered the following assumptions in the power calculations. Assuming that 30% of study subjects in the intervention arm agree to participate in the intervention, we randomized 700 individuals

to each of the intervention and control groups in order to achieve 80% power to detect an average change in HbA1c of 0.5% between the intervention and control groups at an alpha threshold of 0.05 with a HbA1c standard deviation=1.9 (the most commonly cited value in the literature for HbA1c), accounting for 25% rate of loss-to-follow-up.^{1,2} We used Proc Power in SAS 9.4 (Cary, NC) using a t-test and adjusted the sample size to account for the reach rate. Because patients may change insurance, in particular at the end of the calendar year, we accounted for a rate of non-differential loss-to-follow-up of 25% rate. There may also be patients who do not have follow-up HbA1cs, despite restricting to patients whose providers have at-risk contracts with Horizon Blue Cross Blue Shield. As described later in Section 3, we will use multiple imputation methods to account for patients with no follow-up HbA1c values. In addition, this proportion of patients who agree to participate in this intervention has been observed in prior studies that have used a similar approach.²⁵ Finally, the proposed difference of HbA1c of 0.5% is the level that clinical guidelines consider to be a clinically meaningful difference in glycemic control. This HbA1c difference has also been observed in prior work with clinical pharmacists.⁸ Because the primary outcome is HbA1c change, we expect to see clinically meaningful differences in these levels within the 11 to 12-month follow-up period.^{3,4}

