4. ANALYSIS METHODS

4.1 General principles

The primary objective is to examine whether a two-stage process of shared decision-making and behavioral interviewing improves glycosylated hemoglobin (HbA1c) control and medication adherence among patients who have poorly-controlled diabetes. This is a superiority trial.

The primary outcome is pre to post change in mean HbA1c level from baseline to the follow-up period. There is only one primary outcome, so there will be no multiple testing adjustments.

The primary and secondary outcomes will be evaluated using intention-to-treat principles among all assigned patients. Within the intervention group, patients who choose to speak with a pharmacist may differ from those who do not, and an intention-to-treat analysis in this randomized study ensures unbiased comparisons to the control group.

For all outcomes, statistical significance is defined based on $p < 0.05$ level and using two-sided steps. For continuous data, we will present the results as n and mean (standard deviation). For binary data, we will present the data as n (%). We further describe the analysis of and tests used for each of the outcomes in Section 4.2.

The secondary objective is to develop prediction models and examine their ability to predict response to the study intervention based on baseline patient characteristics, such as sociodemographic, clinical, and medication use characteristics, as well as initial receptiveness to changing health behaviors. We will describe the analysis of this objective further in Section 4.2.

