4.2 Analysis methods

4.2.1 Primary objective (Effectiveness of intervention):

Baseline characteristics:

We will measure key baseline characteristics in the 12-months prior to randomization in the pharmacy and medical claims data and enrolment files. These characteristics will include sociodemographic characteristics, such as age and sex, which will be measured in the enrolment files. We will also measure baseline clinical characteristics such as the presence of coronary artery disease, chronic obstructive pulmonary disease, asthma, hypertension, hyperlipidemia, congestive heart failure, depression, liver disease, chronic kidney disease, osteoporosis and prior macrovascular complications. These will be measured in medical claims files using ICD-10 codes. We will also measure the type of oral glucose-lowering agent used in the baseline period (e.g., medical class), average PDC at baseline, and whether or not the medication is branded. We will also measure patients' latest copayments for oral glucose-lowering agents in the baseline period. Finally, we will also measure baseline healthcare resource utilization variables as characteristics including the number of days hospitalized and the number of physician office visits.

We will report, in tabular format, the means and frequencies of baseline characteristics prior to assignment separately for patients in the intervention and control groups and compare these values using t-tests, chi-square tests, and their non-parametric analogues, as appropriate. We will provide absolute standardized differences between the two treatment groups.

Primary analyses:

Primary outcome (change in HbA1c): In the primary analysis, the primary outcome, mean change in glycemic control, will be compared using generalized estimating equations with an identity link function (as a continuous variable) and normally distributed errors within the imputed full analysis set, as described above. Data will be presented as the unadjusted absolute difference in the change in HbA1c between the groups along with 95% confidence intervals.

Secondary outcome (proportion achieving glycemic control)

1) *Proportion of patients achieving optimal glycemic control* (defined by HbA1c < 8): This outcome will be compared using generalized estimating equations with a logit link and binary distributed errors. Data will be presented as the unadjusted odds ratio for optimal glycemic control between the groups along with 95% confidence intervals.

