Secondary outcomes (medication adherence):

1) *Mean PDC in each study arm:* This outcome will be compared using generalized estimating equations with an identity link function and normally distributed errors. Data will be presented as the unadjusted absolute difference between the groups along with 95% confidence intervals.

2) *Proportion of patients achieving optimal adherence* (defined by ≥ 0.80 PDC): This outcome will be compared using generalized estimating equations with a logit link and binary distributed errors. Data will be presented as the unadjusted odds ratio for optimal adherence between the groups along with 95% confidence intervals.

Secondary analyses:

Healthcare resource utilization and spending: Secondary analyses of healthcare resource utilization will use a similar approach as the primary analysis among the full analysis set, except that we will use log link functions with Poisson errors to describe the count data. Health spending will also be evaluated with variances proportional to the mean (e.g., Poisson-like errors) using log-link functions in generalized estimating equations, which has been found to describe insurer healthcare spending data accurately based on prior research.⁵ Data will be presented as the unadjusted odds ratio along with 95% confidence intervals.

Adjusted analyses: If there are differences in baseline characteristics between study groups that are believed to be confounders (defined by a standardized mean difference of >0.1), we will repeat all of our analyses for the primary and secondary outcomes after adjusting for these covariates in multivariable regression. We will present these as adjusted effect estimates along with 95% confidence intervals.

Interactions: We will also explore any potential differences in effectiveness by the specific pharmacist delivering the intervention by evaluating effect measure modification and using interaction terms within the main model for the primary outcome of change in HbA1c. We will present p-values for interactions.

Subgroups: Subgroup analyses of the primary outcome (change in HbA1c) will also be performed for key subgroups, according to age, sex, depression, and baseline medication adherence levels. These analyses will be performed separately among subgroups of the characteristics and compared between the treatment arms. Data will be presented as unadjusted absolute differences in the change in HbA1c along with 95% confidence intervals.

Sensitivity analyses:

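### The exploratory pharmacist interaction in SAP 4.2.1 is mis-specified: crossed with arm it is aliased, and the version that can be fitted compares each pharmacist's patients with non-participants

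*SAP*

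**What the plan says.** SAP 4.2.1, under Interactions, plans to examine effect differences "by the specific pharmacist delivering the intervention by evaluating effect measure modification and using interaction terms within the main model" for change in HbA1c and to give p-values. SAP 3.1 announces the same exploration. The main model is the primary comparison of arms: a GEE with identity link and "normally distributed errors within the imputed full analysis set". The SAP names no cluster unit, working correlation or pharmacist term for it.

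Protocol 3.3 identifies the 700 comparison patients "as a control group for analyses purposes only; these patients will not be contacted". In the intervention arm, a pharmacist delivers the intervention only to patients who are reached and consent. The protocol (8.2) plans on 45% and the SAP (1.3) on 30%. SAP 2.1 and 4.1 both say that patients who choose to speak with a pharmacist may differ from those who do not.

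The only allowance for clustering in either document is the 1.03 factor in protocol Table 5. It is for primary care clinics and is described as non-differential between the groups.

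**The concern.** An interaction asks whether the arm difference varies across levels of another factor. That requires each level to occur in both arms. Here no control has a delivering pharmacist, and more than half of the intervention arm is expected to have none. The SAP does not say how the term is to be coded for these patients, and the coding decides what the p-value tests.

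At stake is a listed result that could be read as evidence that some pharmacists did better than others when it shows only that participants differ from non-participants. A secondary matter is whether outcomes correlated within pharmacist, in one arm only, would make the primary interval too narrow.

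**Working it through.** **The plan's own figure.** Protocol 8.2 sizes the trial "assuming an $\alpha=0.05$, $1-\beta=0.80$, A1c standard deviation=1.9" for a 0.5-point difference. A two-sided two-sample t-test gives 228 per arm. Then 228 × 1.03 = 234.8, 234.8 / 0.75 = 313.1, and 313.1 / 0.45 = 695.8, which agrees with "45% reach rate and 25% LTF: 696 patients/arm". No pharmacist term enters this calculation.

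**Inputs.**
- From the documents: SD 1.9 (variance 3.61); 700 per arm less 25% loss = 525; share treated p = 0.30 or 0.45, so about 158 or 236 treated patients with data; two-sided 0.05.
- Assumed, because the documents do not give them: number of pharmacists k, pharmacist intra-cluster correlation (ICC), and the difference d between participants and non-participants.

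**Step 1: the crossed interaction.** Take five pharmacists, plus a 'none' level for controls and non-participants. Intercept, arm and pharmacist terms make 7 columns of rank 7. Adding arm-by-pharmacist terms makes 12 columns, still of rank 7. The interaction has zero degrees of freedom.

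**Step 2: arm-by-pharmacist terms without pharmacist main effects.** This gives 7 columns of rank 7, so it can be fitted. The coefficients then mean:
- intercept: control mean;
- arm: non-participants minus controls;
- term j: patients of pharmacist j minus non-participants.

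The joint test that all five terms are zero (5 degrees of freedom) asks whether participants equal non-participants as well as whether pharmacists are alike.

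**Step 3: how far that test misleads.** Let all five pharmacists be identical. The non-centrality of the joint F test is λ = (d² / 3.61) × n_c(525 − n_c) / 525, where n_c = 525p is the number treated.

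| Share treated | n_c(525 − n_c)/525 | λ, d = 0.3 | Rejects | λ, d = 0.5 | Rejects |
|---|---|---|---|---|---|
| 30% | 110.3 | 2.75 | 20% | 7.6 | 54% |
| 45% | 129.9 | 3.24 | 24% | 9.0 | 62% |

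Simulation gave matching rates. A test of equality among pharmacists within treated patients stayed near 5%.

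**Step 4: possible effect on the primary standard error.** With pharmacist effects in treated patients only,

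Var = 2 × 3.61/525 + ICC × 3.61 × (p²/k − p/525).

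The first term is 0.01375, a standard error of 0.117. For p = 0.45, k = 5, ICC = 0.05 the second term is 0.1805 × (0.0405 − 0.00086) = 0.00716. The standard error becomes √0.02091 = 0.145, which is 23% larger. Coverage of a nominal 95% interval falls to 88.8%, and simulation also gave 88.8%.

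Over k = 3 to 20 and ICC 0.01 to 0.05:

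| Pharmacists | Standard error larger by, p = 0.30 | p = 0.45 |
|---|---|---|
| 3 | 4% to 18% | 8% to 37% |
| 5 | 2% to 11% | 5% to 23% |
| 10 | 1% to 5% | 2.5% to 12% |
| 20 | 0.5% to 2.5% | 1% to 6% |

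At the extremes, coverage is about 95% and 85%.

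**Step 5: a remedy to avoid.** A mixed model with a random pharmacist effect for contacted patients, and arm as the only fixed effect, gives contacted patients less weight. With p = 0.45, k = 4, ICC = 0.05 there are 59.1 patients per pharmacist and a design effect of 1 + 58.1 × 0.05 = 3.90. The contacted share of the intervention mean falls from 45% to (236.25/3.90) / (236.25/3.90 + 288.75) = 17%. In simulated REML fits with a 1.0-point benefit in contacted patients, the raw intention-to-treat difference averaged −0.44 and the model's arm effect −0.05. The random effect absorbs the treatment effect.

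**The case against.** The strongest reply is that the SAP mentions only interaction terms and no pharmacist main effects, so the term need not be aliased. That is right. A reader might infer that pharmacist differences cannot be estimated at all, and the documents do not support this: terms nested in the intervention arm are estimable. What stands is that the estimable version has non-participants as its reference, and the SAP gives no contrast that removes them.

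A reader might also infer that the SAP expects pharmacists to differ, that the primary GEE treats patients as independent, and that its interval is therefore too narrow. None of this is established. The SAP speaks only of potential differences. The cluster unit is unstated, so independence is an inference from silence, although a plausible one with a single change score per patient. The number of pharmacists and the ICC are not given, partial uptake dilutes any effect, and the narrowing does not arise in the same way if inference is limited to the pharmacists who took part. Clustering would matter more for the as-treated comparison, but SAP 2.1 keeps that out of the primary analyses.

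Finally, the analysis is labelled exploratory. That limits the harm but does not make the p-value interpretable.

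**Conclusion.** The pharmacist interaction is wrong as written, and the matter is minor. Crossed with arm, it adds nothing to the pharmacist terms. In the form that can be fitted, it tests participation together with pharmacist differences. The false-signal rates of 54% to 62% rest on an assumed 0.5-point difference between participants and non-participants, equal in size to the design difference. At 0.3 they are 20% to 24%. Such a difference could come from consent selection, or from a benefit that is the same for every pharmacist.

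The primary intention-to-treat estimate is not affected. Whether its interval is too narrow, and by how much, cannot be known from the documents. The range of 0.5% to 37% on the standard error describes the assumed inputs and is not a finding about this trial.

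**What to change.** - Replace the interaction with an exploratory test of heterogeneity among pharmacists within treated intervention patients only, adjusted for baseline HbA1c. Report the number of pharmacists and the between-pharmacist variance with its interval.
- Keep the primary intention-to-treat estimate unchanged, and state the GEE cluster unit.
- If pharmacist clustering is examined as a sensitivity analysis, use a method that preserves the intention-to-treat contrast. One is an independence working correlation with a small-sample-corrected cluster-robust variance, with pharmacist as the cluster for treated patients and every other patient a singleton. The other is a partially nested model with a fixed contact-status term, recombined to the intention-to-treat contrast. Do not report the primary difference from a model that has a random pharmacist effect but no contact-status term.

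The cost is a few sentences in the SAP and one or two extra models. The call data must carry a pharmacist identifier. SAP 3.4 does not say that they do, but the analysis already planned needs one. With few pharmacists the variance estimate will be imprecise. The documents do not describe how patients are allocated to pharmacists, so differences may reflect case mix and the analysis should stay exploratory.

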For each outcome (e.g., $HbA1c < 8\%$ and $PDC \geq 0.80$), we will first estimate a model that includes only demographic and clinical characteristics. We will then estimate additional models that include these predictors as well as baseline medication adherence. Receipt of the pharmacist intervention will be tested using an interaction term so the logistic regression will provide estimates on all patients and not just those receiving the intervention. We will also repeat the analyses among the subgroup of intervention patients who had at least 1 telephonic encounter with a pharmacist to examine which set of characteristics are most predictive of the response to the intervention. Model estimation will be repeated among relevant patient subgroups (e.g., gender, age) to see if there are any differences in predictive ability.

Models among each of the control and intervention groups will be predicted using both logistic regression and generalized boosting regression, a data mining technique that generates a prediction model through building many regression trees with the potential for many interactions among the predictors.¹⁸ Through these many regression trees, the model can incorporate a number of non-linear associations between the predictors and the outcomes; this approach is considered to be one of the best prediction approaches. Alternative methods of clustering patients who are most likely to respond will also be explored, including machine learning to develop models algorithmically, to partition patients into clusters that have a similar likelihood of experiencing the clinical outcomes.¹⁹

Model accuracy:

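### Subgroup effects on HbA1c change are to be estimated in separate analyses, with no treatment-by-subgroup interaction estimate or test, so the plan cannot show whether the effect differs between subgroups

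*SAP*

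**What the plan says.** The Subgroups paragraph of SAP 4.2.1 plans analyses of change in HbA1c "according to age, sex, depression, and baseline medication adherence levels". On method it says: "These analyses will be performed separately among subgroups of the characteristics and compared between the treatment arms". On presentation: "Data will be presented as unadjusted absolute differences in the change in HbA1c along with 95% confidence intervals". It gives no cut-points for age or adherence, and no estimate or test of the difference between subgroup effects.

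The Interactions paragraph just before it does use the appropriate tool, but for another question. It will "explore any potential differences in effectiveness by the specific pharmacist delivering the intervention by evaluating effect measure modification and using interaction terms", and adds: "We will present p-values for interactions".

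In the prediction aim, SAP 4.2.2 states: "Receipt of the pharmacist intervention will be tested using an interaction term". That sentence concerns logistic models for HbA1c below 8% and PDC of at least 0.80.

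SAP 4.1 sets one threshold for every outcome: "statistical significance is defined based on $p < 0.05$ level and using two-sided steps". It makes no multiplicity adjustment, on the ground that there is a single primary outcome.

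**The concern.** Whether the effect differs between two subgroups is a question about a difference of differences. An interval for men and an interval for women, each from its own analysis, do not answer it. One may exclude zero and the other include it when the true effect is identical in both, simply because each subgroup has fewer patients than the whole trial.

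At stake is the interpretation, not the primary result. The protocol synopsis and Section 1.2 give finding out who benefits, and targeting accordingly, as a purpose of the study. With a 0.05 threshold in general use and no interaction result on the page, side-by-side subgroup intervals on the primary outcome could be read as identifying responders.

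**Working it through.** **Does another planned analysis answer the question?**

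- The pharmacist interaction (SAP 4.2.1) concerns who delivers the calls, not patient characteristics.
- The Aim 2 interaction (SAP 4.2.2) is with receipt of the intervention, in prediction models for two dichotomous outcomes. Even if receipt is taken to mean assigned arm, the outcome is not change in HbA1c.
- SAP 4.2.2 also models change in HbA1c as a secondary prediction analysis, but judges those models by R-squared. It does not contrast the arms by subgroup.

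So nothing planned estimates how the randomized effect on HbA1c change varies with the four characteristics.

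**The plan's own sample size.** Inputs (Protocol 8.2, Table 5): difference 0.5, SD 1.9, two-sided alpha 0.05, power 0.80. The normal formula gives 2 × (1.96 + 0.84)² × 1.9² / 0.5² ≈ 227 per arm, and the exact t-test gives 228, as stated. Then 228 × 1.03 = 235, and 235 / 0.75 / 0.45 = 696, as stated. The SD and alpha used below are therefore the plan's.

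**Inputs for the check.**

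- Evaluable patients per arm: 700 × 0.75 = 525 (SAP 1.3).
- Overall standard error: 1.9 × √(2/525) = 0.117.
- Uniform true effects: 0.5 (the planned difference); 0.5 × 0.45 = 0.225 (the protocol's reach rate, assuming no effect in patients not reached); 0.5 × 0.30 = 0.15 (the SAP's participation rate, same assumption); and 0.33, which is 2.80 × 0.117, the effect giving 80% overall power. The last figure is not in the documents.
- Subgroup shares are not in the documents. Even splits and a 20/80 split are assumed.

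**Formula.** With θ = effect / 0.117, a subgroup holding share f of patients has power p = Φ(θ√f − 1.96). The chance that exactly one of two subgroups is significant is p₁(1 − p₂) + p₂(1 − p₁). For an even split this is 2p(1 − p), which cannot exceed 0.50.

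The last column was simulated (200,000 trials, four independent two-level factors, assumed prevalences 50/50/20/50%). It gives the chance that at least one factor has exactly one significant level.

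| Uniform effect | Overall power | Power in each half | Exactly one half significant | Exactly one, 20/80 split | At least one of four factors |
|---|---|---|---|---|---|
| 0.15 | 25% | 0.146 | 25% | 26% | 49% |
| 0.225 | 48% | 0.273 | 40% | 43% | 68% |
| 0.33 | 80% | 0.512 | 50% | 61% | 84% |
| 0.50 | 99% | 0.854 | 25% | 52% | 66% |

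With no effect anywhere, one even split is discordant in 2 × 0.05 × 0.95 = 9.5% of trials, and at least one of four factors in about 25%.

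**The comparator.** An interaction test has a 5% false-positive rate per factor whatever the overall effect. For any of four, unadjusted, it is 1 − 0.95⁴ = 18.5%, and the simulation agrees.

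**Sensitivity to sample size.** If all 700 per arm carried full information, the even-split figures would be 30%, 45% and 12% at 0.15, 0.225 and 0.50.

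**Power of the interaction test.** Each half has standard error 0.117 × √2 = 0.166, so the difference between halves has 0.166 × √2 = 0.235. Power of 80% needs 2.80 × 0.235 = 0.66 points.

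**The case against.** The strongest reply is that the SAP never says it will classify subgroups by significance. It promises estimates with confidence intervals and no subgroup p-values, and a careful reader can judge heterogeneity from overlapping intervals. The analyses sit under secondary analyses, and conclusions about targeting are meant to come from the prediction aim, which is cross-validated. This stands to the extent that the risk is one of misreading. It would be wrong to infer that the plan itself would produce false claims about who benefits. It does not remove the gap, because overlap judged by eye is a poor substitute for an estimated difference, and the prediction aim makes no randomized comparison of this outcome by subgroup.

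Two stronger readings of the numbers are tempting and should be resisted.

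- A reader might infer that a uniform effect will usually appear to work in one group only. For one evenly split factor this cannot be so, since 50% is the ceiling, and at the plan's 0.5 difference the figure is 25%. It passes half only for uneven splits, for several factors taken together, or after conditioning on a significant overall result when overall power is about 80% or less (57% for one even split at exactly 80%).
- A reader might set the any-of-four rates against 5%. The like-for-like figure is about 19%. With no effect at all the contrast is small, 25% against 19%. The 25% also counts subgroups significant for harm; a false benefit in exactly one level of some factor occurs in about 13% of simulated trials.

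It is also fair that unadjusted interaction tests keep that 19%, so the change limits the problem but does not eliminate it.

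**Conclusion.** The point holds as a gap in the method. The SAP states a specific approach for the four patient subgroups, and that approach cannot establish that effects differ, although interaction terms are already planned in the same section for the pharmacist question.

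For one evenly split factor and a real uniform effect, the rate of discordant significance is about 25-50%, five to ten times that of an interaction test. Across the four factors it is about 2.6 to 4.5 times the like-for-like 19% (49/19 to 84/19). With no effect the excess is modest.

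These sizes rest on 525 evaluable per arm, equal SD of 1.9, independent factors, a normal approximation without clustering, and subgroup shares that the documents do not give. The lowest even-split figure with a real effect, 12%, needs all 700 per arm fully informative and the whole 0.5 difference realised. The case for an interaction estimate does not depend on any of these figures.

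**What to change.** In the Subgroups paragraph of SAP 4.2.1:

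1. Add an arm-by-characteristic interaction term to the primary GEE model on the imputed full analysis set, one characteristic at a time.
2. Report the difference in effects with its 95% CI and interaction p-value as the heterogeneity result, alongside the subgroup estimates already planned.
3. Include the same interaction terms in the imputation model of SAP 3.1. Follow-up HbA1c is imputed for those without a value, and imputing without these terms pulls subgroup differences towards zero.
4. Label the results exploratory, with no multiplicity control.

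Modelling age and baseline PDC as continuous is optional. It avoids cut-points but adds a linearity assumption. If categories are kept, state them in advance.

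The cost is a few sentences in the SAP and a few lines of model code. The downside is low power: most of these tests will be inconclusive, and the report should say that a non-significant interaction does not show equal effects.
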